#### **Requirements for E2112 site registration:**

- CTSU IRB Certification (for sites not participating via the NCI CIRB)
- CTSU IRB/Regulatory Approval Transmittal Sheet (for sites not participating via the NCI CIRB)

### Required Protocol Specific Regulatory Documents

1. Copy of IRB Informed Consent Document.

**NOTE:** Any deletion or substantive modification of information concerning risks or alternative procedures contained in the sample informed consent document must be justified in writing by the investigator and approved by the IRB.

2. A. CTSU IRB Certification Form.  
**Or**  
B. Signed HHS OMB No. 0990-0263 (replaces Form 310).  
**Or**  
C. IRB Approval Letter

**NOTE:** The above submissions must include the following details:

- Indicate all sites approved for the protocol under an assurance number.
- OHRP assurance number of reviewing IRB
- Full protocol title and number
- Version Date
- Type of review (full board vs. expedited)
- Date of review.
- Signature of IRB official

### Checking Your Site's Registration Status:

Check the status of your site's registration packets by querying the RSS site registration status page of the members' section of the CTSU website. (Note: Sites will not receive formal notification of regulatory approval from the CTSU Regulatory Office.)

- Go to <https://www.ctsu.org> and log in to the members' area using your CTEP-IAM username and password
- Click on the Regulatory tab
- Click on the Site Registration tab
- Enter your 5-character CTEP Institution Code and click on Go

**NOTE:** The status given only reflects compliance with IRB documentation and institutional compliance with protocol-specific requirements outlined by the Lead Network. It does not reflect compliance with protocol requirements for individuals participating on the protocol or the enrolling investigator's status with the NCI or their affiliated networks.

### Patient Enrollment

#### Treatment must start within ten working days of randomization.

Patient enrollment will be facilitated using the Oncology Patient Enrollment Network (OPEN). OPEN is a web-based registration system available on a 24/7 basis. To access OPEN, the site user must have an active CTEP-IAM account (check at [Rev. 4/15](https://eapps-

<div data-bbox=)

[ctep.nci.nih.gov/iam/index.jsp](http://ctep.nci.nih.gov/iam/index.jsp)) and a 'Registrar' role on either the LPO or participating organization roster.

All site staff will use OPEN to enroll patients to this study. It is integrated with the CTSU Enterprise System for regulatory and roster data and, upon enrollment, initializes the patient in the Rave database. OPEN can be accessed at <https://open.ctsu.org> or from the OPEN tab on the CTSU members' side of the website at <https://www.ctsu.org>.

Prior to accessing OPEN site staff should verify the following:

- All eligibility criteria have been met within the protocol stated timeframes.
- All patients have signed an appropriate consent form and HIPAA authorization form (if applicable).

**NOTE:** The OPEN system will provide the site with a printable confirmation of randomization and treatment information. Please print this confirmation for your records.

Further instructional information is provided on the CTSU members' web site OPEN tab or within the OPEN URL. For any additional questions contact the CTSU Help Desk at [name] or [[contact]](mailto:[contact]).

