## 5. Treatment Plan

### 5.1 Administration Schedule

Cycle = 4 weeks (28 days)

Rev.4/15

A complete cycle of treatment is defined as 28 days ( $\pm$  3 days) of once daily continuous treatment of exemestane in combination with entinostat/placebo. A new cycle start is defined as the first planned date of entinostat/placebo for the cycle.

Rev. 10/16

Entinostat/placebo should be taken on an empty stomach, at least 1 hour before and 2 hours after a meal/snack. Missed doses should not be made up later.

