#### 5.6.4 PRO Administration Instructions

All PRO questionnaires will be administered as a paper survey. Ideally, participants will complete questionnaires at the time of scheduled study visits. For the first assessment (Cycle 1), PRO should be administered prior to the administration of study drug. With the exception of the 8-item FBSI, PRO time points overlap with protocol-specified clinic visits. If the 8-item FBSI does not overlap with protocol-specified clinic visits and/or if PRO assessments are not administered in clinic, the study questionnaires will be mailed to participants who will be asked to complete questionnaires and return by mail to clinic. After 7 days, clinic or research staff may contact participants by telephone and ask participants to complete the questionnaire on paper and then read their answers over the telephone to the staff person.

In the event that the 8-item FBSI for TTD endpoint is being assessed at a protocol-specified clinic visit that includes an evaluation for progression, questionnaires will be completed before participants discuss disease status with health-care professionals. This will minimize potential bias, and is modeled after the study by Rini et al.

For the post-end of treatment PRO, we propose to administer to participants who return to clinic via paper. In the event that a participant does not return to clinic for a visit after end of treatment, we will collect the PROs via telephone. This will compensate for potential responder bias, wherein healthier patients are more likely to return to clinic and thus, to complete the post-treatment surveys. In collecting PRO data via phone, the survey will be mailed to the participant, who will complete it and then read their responses to the interviewer. This procedure will minimize mode effect, whereby participants report less symptoms burden during phone or in-person

interviews than with written surveys. This approach will approximate the completion of PROs in clinic as closely as possible.

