**NOTE:** Height measurements may have been taken > 4 weeks from baseline.
- CBCs, which includes WBC, ANC, Platelets, Hgb, and Hct required for protocol therapy must be done ≤ 72 hours prior to Cycle 2 and every cycle thereafter. Baseline CBCs do not need to be repeated prior to Cycle 1 Day 1.
- Albumin, alkaline phosphatase, total bilirubin, bicarbonate, BUN, calcium, chloride, creatinine, glucose, magnesium, phosphorus, potassium, total protein, SGOT (AST), SGPT (ALT), sodium must be done ≤ 72 hours prior to Cycles 2-4 and every 3 cycles thereafter. Baseline chemistries do not need to be repeated prior to Cycle 1 Day 1.
- Only required for women age < 55 years and with intact ovaries as described in Section [3.1](#).
- Baseline bone scan required in all patients.  
**NOTE:** If bone scan done ≤ 6 weeks prior to registration showed no evidence suggesting bone metastases and no clinical indication of skeletal pain or other evidence suggesting bone metastases, a repeat baseline bone scan is not required.
- CT of the chest and CT or MRI of abdomen/pelvis are required at baseline. Subsequent imaging for the subject should be conducted on the same scanner using the same acquisition and reconstruction parameters. Those tests required to follow known site(s) of disease must be repeated at the end of 12 weeks from randomization and then every 12 weeks (3 cycles) during treatment and according to the follow up schedule if off treatment, until first progression of disease. **NOTE:** All tumor assessment should be scheduled based on calendar time (every 12 weeks) and not cycle length. Image thickness (reconstructed) should be 5 mm or less for CT and MRI, and contiguous slices are preferred to those with intervening gaps. Consistent use of contrast agent, dose, and injection parameters (including time of image collection after contrast) are recommended. See Section [10](#) for additional details and submission instructions.  
**NOTE:** If the CT of the chest and CT or MRI of abdomen/pelvis done ≤ 6 weeks prior to randomization showed no evidence of disease in the area(s) and no clinical indication suggesting new metastases, full re-staging including all areas is not required; however, ensure that disease is evaluable per RECIST 1.1 requirements (Section [6](#)).
- Patient-Reported Outcomes to be assessed at the following time (see Section [5.6](#) for detailed instructions):

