PROMIS Fatigue, FAACT, FACIT-D: Baseline (before Cycle 1 Day 1), end of Cycle 3, end of Cycle 6, end of Cycle 12, at end of protocol treatment, including treatment discontinuation for any reason (i.e., toxicity, progression, completion of protocol therapy) and 4 weeks after end of protocol treatment, including treatment discontinuation for any reason (i.e., toxicity, progression, completion of protocol therapy).

Rev. 10/16 The ECOG-ACRIN Medication Adherence Scale Modified from the Morisky Index: end of Cycle 3, end of Cycle 6, end of Cycle 12, and at  
Rev. Add7 end of protocol treatment, including treatment discontinuation for any reason (i.e. toxicity, progression, completion of protocol therapy).  
Please note there will be one Medication Adherence Scale form completed for each agent (entinostat/placebo and exemestane).

FACT-G: Baseline (before Cycle 1 Day 1), end of Cycle 3, end of Cycle 6, end of Cycle 12, and at end of protocol treatment, including treatment discontinuation for any reason (i.e. toxicity, progression, completion of protocol therapy).

8. The FBSI will be administered at baseline, end of each cycle for the first six months after randomization, and then at the end of Cycles 8, 10, and 12. After Cycle 12, the FBSI will be administered on the same schedule as Tumor assessments until disease progression.
9. Pill counts for entinostat/placebo and diaries for exemestane should be collected at the end of each cycle until discontinuation of study treatment.
10. Repeat any test not done  $\leq$  the prior 28 days.
11. Every 3 months if patient is  $< 2$  years from study entry, every 6 months if patient is 2-5 years from study entry, and annually if patient is  $>5$  years from study entry. No specific requirements if patient is more than 10 years from study entry.
12. Tumor assessments are to be done up to (and including) the assessment which shows first progression of disease. If patient discontinues treatment due to reasons other than disease progression, concomitant medication and tumor assessments should be performed until disease progression on the following schedule: Every 3 months if patient is  $< 2$  years from study entry, every 6 months if patient is 2-5 years from study entry, and annually if patient is  $>5$  years from study entry. No specific requirements if patient is more than 10 years from study entry.

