13. Submit blood samples to the [name] Laboratory from patients who answer "Yes" to "I agree to participate in the laboratory research studies that are being done as part of this clinical trial." Baseline blood samples should be collected after randomization, prior to start of treatment on Day 1 (preferably within 2 days of Day 1). Day 15 blood samples should be collected prior to entinostat/placebo dose on that day.  
**NOTE:** Do not start treatment on Fridays as the baseline and day 15 blood collections cannot be shipped on Fridays.  
Submit optional blood and tissue samples for future research to the ECOG-ACRIN Central Biorepository and Pathology Facility (CBPF) from patients who answer "Yes" to "I agree to provide additional specimens for research."
- Rev. 10/16 14. All specimens submitted must be entered and tracked via the online ECOG-ACRIN Sample Tracking System (STS). The exact date and time of entinostat/placebo administration and of PK plasma sample collection must be entered into the STS.
- Rev. 10/16 15. Kits are available for blood collection and shipment. Kit order instructions are provided in Appendix VI. Kit orders will, on average, be delivered within 3 business days from time of order placement.
16. PRO-CTCAE items will be administered at Baseline, end of each Cycle, and at end of protocol treatment, including treatment discontinuation following the same schedule as trial Symptom/Toxicity assessments.
17. Concomitant Medications will be collected up to 90 days from the end of study treatment.
18. A complete cycle of treatment is defined as 28 days ( $\pm 3$  days) of once daily continuous treatment of exemestane in combination with entinostat/placebo. A new cycle start is defined as the first planned date of entinostat/placebo for the cycle.

Rev. 10/16  
Rev. 9/17

19. Pre/perimenopausal females must have commenced treatment with LHRH agonist at least 4 weeks prior to randomization. If patients have received alternative LHRHR agonist prior to study entry, they must switch to goserelin for the duration of the trial.
20. For all women of child bearing potential, must be done  $\leq$  2 weeks prior to randomization.

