## 9.6 Patient-Reported Outcomes Assessment

There are two objectives in the patient-reported outcomes (PROs) assessment study. The first objective is to compare overall HRQL between treatment arms. The second objective is to compare symptoms associated with entinostat between arms. The type I error rate is equally split between the two objectives to control the overall one-sided type I error at 2.5% for the PROs analysis. In order to provide sufficient power for the two objectives, all 360 patients included for the PFS endpoint on the main study and receive at least one dose of protocol therapy (i.e., all treated patients) will be eligible for the PROs study. PROs will

not be evaluated on the additional 240 patients primarily enrolled for the OS endpoint.

Rev. Add7

With the exception of the FBSI and the Medication Adherence Scale, the PROs assessment will be administered at the following time points: baseline, 3, 6, and 12 months (the timing of these assessments coincides with the first, second and fourth disease assessments), at the end of protocol treatment/time of protocol treatment discontinuation and 4 weeks after protocol treatment is discontinued. Given that anticipated median survival is about 2 years and median PFS is about 4-7 months, the 3-month assessment is expected to provide the best assessment of treatment-emergent symptoms. Hence the primary comparison of PROs between treatment arms is based on the month 3 assessment.

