10.1.11 On-Treatment Imaging

Following randomization into the trial, subjects will be imaged at the end of 12 weeks from randomization and then every 12 weeks thereafter until disease progression. Additionally, subjects will be imaged within 28 days of treatment discontinuation.

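### Tumor scans run from randomization but the main PRO forms run from first dose, and no rule keeps a patient whose week-12 scan shows progression in the month-3 PRO comparison

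*Combined protocol and SAP*

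**What the plan says.** **Scan clock.** Section 10.1.11 states that "subjects will be imaged at the end of 12 weeks from randomization and then every 12 weeks thereafter until disease progression". Footnote 6 of Section 7 adds "All tumor assessment should be scheduled based on calendar time (every 12 weeks) and not cycle length". Neither gives a scan window or a time for telling the patient the result.

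**PRO clock.** Footnote 7 of Section 7 lists "FACT-G: Baseline (before Cycle 1 Day 1), end of Cycle 3, end of Cycle 6, end of Cycle 12". PROMIS Fatigue, FAACT and FACIT-D are due at the same cycle ends (Section 5.6.3.2). Section 5.1 fixes the cycle clock: "A new cycle start is defined as the first planned date of entinostat/placebo for the cycle". Footnote 18 of Section 7 says "A complete cycle of treatment is defined as 28 days", with a tolerance of 3 days either way.

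**Gap between the clocks.** Section 4 (Patient Enrollment) says "Treatment must start within ten working days of randomization". Sections 4.1 and 8 say there are no starter supplies, so drug is shipped only after randomization.

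**Claimed alignment.** Section 9.6 says of the 3-, 6- and 12-month PRO assessments that "the timing of these assessments coincides with the first, second and fourth disease assessments". Section 5.6.3 says much the same, and the Section 7 calendar places scans in cycle-end columns.

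**Use in the analysis.** Section 9.6 makes month 3 the primary PRO time point. Progression ends protocol therapy (Section 5.7), as judged by local reads (Section 10.2). The form then due is the end-of-treatment form, which Section 9.6.2 compares between arms as its own time point.

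**Order of form and result.** For the FBSI at a visit that includes a progression evaluation, Section 5.6.4 says "questionnaires will be completed before participants discuss disease status with health-care professionals". It gives PRO-CTCAE a similar rule. It names no such rule for FACT-G, PROMIS Fatigue, FAACT or FACIT-D.

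**The concern.** The plan treats the month-3 form and the first scan as one event, but its own timing rules separate them, with the scan nominally first. Two things follow.

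First, whether a patient has a month-3 form can depend on the scan result. A patient who is in clinic and on treatment at week 12, but whose scan shows progression, may be off protocol therapy before Cycle 3 ends. The next form carries a different label and is left out of the primary PRO comparison. If entinostat delays progression, more of these patients are in arm B, so the month-3 sets would be selected differently by arm. Section 5.6.3 itself warns that PRO data limited to patients still on treatment are biased.

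Second, a form due some days after a scan may be completed after the patient has heard the result, and no rule naming the four main instruments prevents this.

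At stake are the overall HRQL and symptom comparisons (objectives 2.2.5 and 2.2.6). PFS and OS are not affected.

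**Working it through.** **1. The plan's own figure.** Section 9.6.1 gives about 93% power for HRQL with 162 per arm, a difference of 5, SD 12 and two-sided alpha 0.025.

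- Standard error = 12 × √(2/162) = 1.333
- 5/1.333 = 3.75; critical value 2.241
- Power = Φ(3.75 − 2.241) = 0.934 (0.932 by the noncentral t)

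The stated figure reproduces. It rests on 10% attrition in both arms by month 3.

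**2. Lag from randomization to first dose.** The ceiling is ten working days, which is 14 calendar days from any weekday without holidays. For a Monday registration, Section 8 has receipt on Thursday if expedited (day 3). By ordinary US shipping it gives about Wednesday, read here as the following week (day 9). Section 4.1 says within five working days. Start days 3, 9 and 14 are used below, assuming the patient starts on arrival for the first two.

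**3. End of Cycle 3 against the scan.** The scan is at 12 × 7 = day 84 from randomization. Nominal end of Cycle 3 is start day + 3 × 28. The last column assumes that the 3-day tolerance accumulates over three cycles (9 days either way).

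| Start day | Nominal end of Cycle 3 | Days after scan | With tolerance |
|---|---|---|---|
| 3 | 87 | 3 | 78 to 96 |
| 9 | 93 | 9 | 84 to 102 |
| 14 | 98 | 14 | 89 to 107 |

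The form nominally falls 3 to 14 days after the scan. The tolerance can absorb a short lag but not a 14-day one. The same offset carries to months 6 and 12, because 6 × 28 = 168 days is week 24 and 12 × 28 = 336 days is week 48.

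**4. Upper bound on patients affected.** Section 9.2.1 plans exponential PFS with medians of 4.1 months (B) and 7.1 months (A). Day 84 is 84/30.4375 = 2.76 months.

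- Arm B: 1 − 2^(−2.76/4.1) = 37.3%
- Arm A: 1 − 2^(−2.76/7.1) = 23.6%

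The 4.1-month median is from central review, while treatment stops on local reads. The local-review placebo median cited in Section 1.3 is 3.2 months, which gives 1 − 2^(−2.76/3.2) = 45% for arm B.

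**5. What the bound would mean for HRQL power.** These figures use 180 per arm, the planning medians and the noncentral t.

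| Share of patients with a PFS event by week 12 who lack a month-3 form | n in A / B | Power | Power with a further 10% non-response |
|---|---|---|---|
| All | 137 / 113 | 85% | 80% |
| Half | 159 / 146 | 92% | 88% |

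Starting from the 171 treated per arm assumed in Section 9.3.3, the first row becomes 131 / 107, with 83% and 78%. For a symptom effect size of 0.40, where the plan states 80%, the first row (180 per arm, no further non-response) gives 65%.

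These rows bound the loss from progression by the first scan. They do not isolate the part due to the two clocks.

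**The case against.** A reader might infer that month-3 forms are always completed after the scan result is known. The documents do not say that. They set no scan window and no disclosure time, and the cycle tolerance can bring the form of an early starter to or before scan day. Physical exams are scheduled at cycle ends, so the result may be discussed at the visit where the form is due. Such a visit could also count as one with a progression evaluation under Section 5.6.4, and the word used there for the forms could be read to cover every form given that day. Completion after the result is likely for some patients, not established for all.

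A reader might also infer that aligning the clocks would recover every patient with a PFS event by week 12 (about 40 in A and 64 in B of 171 treated). That does not follow. The count includes deaths and earlier progression, which alignment would not change.

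Nor are these patients lost to PRO assessment. All four instruments are due at end of treatment for any reason, and PROMIS Fatigue, FAACT and FACIT-D again four weeks later. Section 5.6.3 offers this as the remedy for selection.

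The two consequences also partly offset each other. If patients with progression leave the month-3 set, most who remain have heard of no progression in either arm, so little knowledge of bad news differs by arm.

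Finally, the point does not extend to every form. FBSI is also described as timed from randomization, and both FBSI and PRO-CTCAE have ordering rules.

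All of this narrows the point. It does not reconcile the scan rule with the claimed alignment, and it does not supply a rule that maps the end-of-treatment form to month 3.

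**Conclusion.** The concern holds in this limited form. The scan rule in Section 7 footnote 6 and Section 10.1.11 conflicts with the alignment claimed in Sections 5.6.3 and 9.6 and implied by the calendar columns. The nominal gap is about 3 to 14 days. As written, a patient whose week-12 scan shows progression before Cycle 3 ends leaves the primary PRO comparison, and more such patients are expected in arm B if entinostat works.

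The size is bounded by 37% (B) and 24% (A). This rests on exponential PFS at the planning medians and on every such patient lacking a month-3 form. The share due to the lag alone cannot be derived from the documents. The unequal selection by arm matters more than the loss of power. It affects secondary endpoints only, but it is cheap to remove and should be corrected.

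**What to change.** In Section 5.6.3 and Section 7 (the calendar and footnote 7), time the month-3, 6 and 12 FACT-G, PROMIS Fatigue, FAACT and FACIT-D forms to the week-12, 24 and 48 tumor assessments counted from randomization. Have them completed on or before the scan and before the result is discussed. In Section 5.6.4, name these four instruments in the ordering rule.

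In Section 9.6, define month 3 as the week-12 form whether or not that scan then ends treatment. State when one form may serve as both the month-3 and the end-of-treatment form. Bring the alignment sentences in Sections 5.6.3 and 9.6 and the calendar columns into line.

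The cost is mainly wording. At month 3 patients would have had about 10 to 11.5 weeks on drug (84 − 14 = 70 days to 84 − 3 = 81 days) and not 12. Some would need an extra form, or a mailing when the scan is not on a clinic day.
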